5.6 Secondary Endpoints

Reduction in length of NICU hospital stay (NICULOS) for all neonates from time of birth up to neonatal discharge in prospective subjects versus controls will be evaluated using a time-to-event analysis in the top quantile of length of stay. To avoid significant contamination of short stays associated with term births, the strata will be adjusted by the

preterm birth rate. If 1.2 times the preterm birth rate in the controls is less than 10%, the quantile will be set at 1.2 times the preterm birth rate. Otherwise the quantile will be set to 10%.

The secondary hypothesis is as follows:

H_0 : no difference between controls and the prospective arm

 NICULOS in PreTRM® test group =

 NICULOS in historical group

H_A : shorter NICULOS in the PreTRM® prospective arm as compared to historical controls.

Statistical testing for this endpoint will be performed using a Cox proportional hazards regression model with covariates and stratification as specified above.

For increase in time of gestation in prospective subjects versus historical controls, we will evaluate it using a time-to-event analysis in the bottom quantile of gestational ages at birth. To avoid significant contamination of short stays associated with term births, the strata will be adjusted by the preterm birth rate. If 1.2 times the preterm birth rate in the controls is less than 10%, the quantile will be set at 1.2 times the preterm birth rate. Otherwise the quantile will be set to 10%.

The secondary hypothesis is as follows. :

H_0 : no difference between controls and the prospective arm

 time of gestation in PreTRM® test group =

 time of gestation in historical group

H_A : longer time of gestation in the PreTRM® prospective arm as compared to historical controls.

Statistical testing for this endpoint will be performed using a Cox proportional hazards regression model with covariates and stratification as specified above.

A secondary endpoint will be met if the endpoint achieves significance with an alpha of 0.05. No adjustments will be made for the multiple hypothesis tests among the secondary endpoints, but conclusions will be interpreted with caution due to the multiple tests proposed.

Non-proportionality of secondary endpoints will be addressed using the pre-specified adjustments for non-proportionality, and the additional approaches provided above for the co-primary endpoint NNOLOS.

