3.6 Secondary Hypothesis or Questions

Women who were screened with the PreTRM® test will have 1) a significant reduction in length of NICU hospital stay for neonates from time of birth up to neonatal discharge or 2) a significant increase in duration of gestation (GAB) in comparison to historical controls.

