From historical data on pregnancies at ChristianaCare Health System, we estimated a historical preterm birth rate of 9.1%. The sample size estimation is based on simulations of co-primary outcomes based on a simulated distribution of gestational age with a singleton preterm birth rate of 9.1%, and an effect of intervention based on literature data²⁶⁻²⁸, with α -level spending of 0.05 shared between co-primaries using Holm's method.

Given shut-down of the study due to the SARS-CoV-2 pandemic, the sample size for the study is estimated to be approximately 1,453 subjects in the prospective arm, and approximately 10,000 in the historical control group. In the primary and alternative analyses, more than 10,000 subjects may meet the eligibility criteria for the historical control group and have the required data, and if so, they will be included in the study.

Power and sample size for this study are affected by factors including the proportion of prospective subjects receiving PreTRM® risk scores at or above the threshold of 16% risk (the study Screen Positive Rate (SPR)), the proportion of higher-risk subjects complying with interventions (compliance), and the rate at which subjects and their neonates remain in the study (retention). For the purpose of power and sample size estimation and based on study monitoring, we estimate that 34% of subjects in the pre-pandemic portion of the prospective arm had PreTRM® risk scores at or above the threshold of 16% risk (the SPR).

Power and sample size are also affected by the study population's baseline level of risk of adverse neonatal outcomes related to prematurity, the sensitivity of testing in identifying at-risk pregnancies, retention of subjects in the study and the efficacy of the interventions as implemented in the study. Literature²⁶⁻²⁸ indicates that the effect of treatment is not constant across different values of GAB. Thus, there is no single value of the effect size in terms of proportion of subjects with NMI less than 3, or mean length of stay. Rather, the effect size is larger for subjects with earlier GAB, while the effect size is reduced for subjects with later GAB.

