Statistical tests will be performed at the 5% significance level unless otherwise specified. Such tests will be two-tailed unless otherwise specified as directional tests. Primary and secondary endpoints will be analyzed using one-tailed tests.

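### The gestational-age secondary endpoint restricts a Cox model to the earliest births, so it selects women on the outcome being tested and leaves the risk set and cut-off undefined

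*SAP*

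**What the plan says.** Section 3.6 states the secondary hypothesis as "a significant increase in duration of gestation (GAB) in comparison to historical controls". Section 5.6 turns this into a test: "we will evaluate it using a time-to-event analysis in the bottom quantile of gestational ages at birth". The reason given is "To avoid significant contamination of short stays associated with term births, the strata will be adjusted by the" preterm birth rate, the same sentence that Sections 5.5 and 5.6 use for the two length-of-stay endpoints. The quantile is 1.2 times the control preterm rate if that is below 10%: "Otherwise the quantile will be set to 10" per cent. The model is a "Cox proportional hazards regression model with covariates and stratification as specified above".

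On the decision rule, Section 5.6 says "A secondary endpoint will be met if the endpoint achieves significance with an alpha of 0.05", with no multiplicity adjustment among secondary endpoints. The opening of Section 5 adds "Primary and secondary endpoints will be analyzed using one-tailed tests".

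The section does not say whether the quantile is that of the controls, of both arms pooled, or of each arm separately. It does not say whether women who deliver later are excluded or censored. It does not define the strata for this endpoint.

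**The concern.** For length of stay, keeping the longest stays discards the short ones. With a fixed cut-off that is left truncation, which a Cox model can handle. For gestation the tail of interest is at the other end. Keeping only the lowest gestational ages is right truncation: every risk set then holds only women already known to deliver before the cut-off. A birth moved past the cut-off is what the screening strategy hopes to achieve, and the restriction deletes it. With a common cut-off, the test compares only the timing among the remaining early births, not how many there are.

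Section 4 makes this matter more. It models treatment as a shift in gestational age at birth (GAB) in which "the effect size is larger for subjects with earlier GAB", so births crossing the cut-off are part of the planned effect.

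A different problem arises if the quantile is taken within each arm. A fixed fraction of each arm is then kept, so prevented births are replaced by the next-earliest ones rather than lost. But the two cut-offs are sample estimates, and the Cox standard error treats them as fixed.

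At stake is whether a secondary endpoint with its own 0.05 criterion is declared met. The preterm birth rate itself is compared only as an exploratory endpoint (Section 5.7).

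**Working it through.** **Inputs from the SAP.** Section 4: control preterm rate 9.1%; 1,453 prospective and about 10,000 historical women; 34% screen-positive; 55% compliance. Section 5.6: the quantile rule. Section 5: one-sided 0.05. The SAP gives neither a GAB distribution nor an effect size for this endpoint, so both are assumed below.

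1. *Quantile.* 1.2 × 9.1% = 10.92%, which is not below 10%, so the quantile is 10%. This lies at or just above 37 0/7 weeks.

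2. *mITT size.* 1,453 × (0.66 + 0.34 × 0.55) = 1,453 × 0.847 ≈ 1,231. Results below use 1,453 or 1,231 against 10,000.

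3. *The plan's nearest figure.* No power is stated for gestation. For length of stay, which uses the same quantile construction, Section 4 states 0.8–1.0 for hazard ratios 1.32–1.46. Schoenfeld's formula is power = Φ(|ln HR| × √(D·p·(1−p)) − z), with D = 10% of all women as events and p the prospective share. For n = 1,453 it gives 0.93 and 0.996 at one-sided 0.05, and 0.88 and 0.99 at 0.025. The stated range is reproduced.

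4. *Hand check for a 30% cut in preterm birth, common 10% cut-off, n = 1,453.* Assume 30% of preterm births become term births. The prospective fraction below the cut-off is then about 0.7 × 9.1% + 0.9% = 7.27%, or about 106 women, against 1,000 controls.
   - All women kept and censored at the cut-off: HR ≈ 7.27/10 = 0.727; D ≈ 1,106; p = 1,453/11,453 = 0.127; √(D·p·(1−p)) = 11.07. Power = Φ(0.319 × 11.07 − 1.645) ≈ 0.97.
   - Restricted to women below the cut-off: the simulated HR shrinks to 0.89–0.92; p falls to 106/1,106 = 0.096; √(D·p·(1−p)) = 9.77. Power ≈ 0.31 at HR 0.89 and 0.20 at HR 0.92.

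5. *Simulation.* Two-group Cox model with Efron ties, no covariates, and four assumed GAB distributions (preterm/term mixture, Gumbel, t4, normal), each set to 9.1% preterm, in continuous time and in whole days. Power is for n = 1,453 and a 30% relative cut in preterm birth; null rates cover both sizes.

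| Analysis | No effect, one-sided rejection | Conversion to term | Smooth shift, larger at early GAB |
|---|---|---|---|
| Control 10% cut-off, restricted | 2.7–4.9% | 21–29% | 11–48% |
| Same cut-off, all women censored | 4.3–5.9% | 94–97% | 98–99% |

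The estimated HR is 0.85–0.94 restricted and 0.68–0.74 with all women. A pooled quantile gives restricted power of 15–35%. A fifth assumed distribution with n = 1,231 gives about 30% against 93% under conversion.

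6. *Dependence on the form of effect (fifth distribution, n = 1,231).* A 7-day delay of every preterm birth gives about 61% restricted and 93% censored. A proportional shift gave 0.2% and 85%. Pure prolongation of early births reverses the order: 93% restricted and 82% censored.

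7. *Quantile taken within each arm, no effect.* The population fraction below a sample 10% quantile has standard error √(0.1 × 0.9/n): 0.79 percentage points for n = 1,453, 0.86 for n = 1,231 and 0.30 for n = 10,000. The model ignores this variation. The simulated one-sided false-positive rate is 26–37% with whole days and 38–42% in continuous time across the four distributions, and about 25–28% under the fifth. With completed weeks it is 24–26% if exactly the lowest 10% are kept, and below 1% if all ties are included. Section 3.7 defines GAB by a difference in days, so day-level data is the relevant case.

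8. *Stratification read as all women stratified by the quantile.* Power is 6–9% under conversion and 4–14% under the smooth shift, apart from one distribution at 82%.

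**The case against.** The strongest reply is that the SAP never says later births are deleted. It speaks of a time-to-event analysis, strata and stratification, and following all women with censoring at the cut-off is not expressly ruled out. On that reading the test is valid and well powered. This stands as a limit on the claim. But censoring is not mentioned for this endpoint, and the stated aim of keeping term births out points to exclusion. If censoring was meant, the text still has to say so.

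Second, nothing says the quantile is taken within each arm; the only rate named is the controls' preterm rate. That also stands. The inflated false-positive rate belongs to one unexcluded reading. It should not be combined with the loss of prevented births, because under per-arm quantiles those births are replaced and power for the 30% cut is about 99%.

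Third, the size depends on the assumed GAB distribution and on how treatment acts, and prolongation can favour the restricted analysis. This is correct, and is why ranges are given.

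Fourth, the endpoint is secondary and outside the Holm family, Section 5.6 promises cautious interpretation, and Section 5.7 tests preterm rates by logistic regression. These limit the consequence, but an exploratory result does not decide whether the secondary endpoint is met.

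A reader might also restrict at 37 0/7 weeks and infer that preventing late preterm births would often look like harm. The SAP does not support this: at a 9.1% preterm rate its rule gives the 10% quantile, not 37 weeks. With the 10% cut-off, when 40% of births at 34–36 weeks were prevented, harm was signalled in under 10% of simulated trials.

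**Conclusion.** The point holds for this secondary endpoint. On its natural reading, Section 5.6 selects women on the outcome under test. With one control-based 10% cut-off, it has about 11–48% power for a 30% cut in preterm birth, where keeping and censoring all women gives about 93–99%. The false-positive rate on that reading is not inflated; the fault is lost sensitivity to the effect of interest.

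The undefined location of the quantile is a second, separate fault: per-arm quantiles would give a one-sided false-positive rate of roughly 25–40% with day-level GAB.

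The 30% effect, the GAB distributions and the absence of covariates are assumptions. The power band is not a bound, since other forms of effect fall outside it and pure prolongation reverses the comparison. It would be too strong to say that the endpoint can never detect a benefit, or that it will often claim one falsely: some signal remains just above 37 weeks, and false claims require the per-arm reading. The co-primary conclusion is not affected by this point.

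**What to change.** Replace the sentence for this endpoint in Section 5.6 so that it states the following:

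- Every mITT woman is in the analysis.
- One cut-off, fixed in days, applies to both arms: either the control-arm quantile from the existing 1.2×/10% rule or 37 0/7 weeks.
- Births up to the cut-off are events; all women undelivered at that point are censored there.
- The Cox model and covariates are unchanged, and HR < 1 means longer gestation.
- The restriction to the bottom quantile is deleted, and the meaning of stratification for this endpoint is stated or the term removed.

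This changes a few lines of wording and needs no new data. The cost is somewhat lower power if treatment only prolongs early births without taking them past the cut-off (82% against 93% in the case examined).

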5.7 Exploratory Analyses

In AVERT, there is a challenge and opportunity in the moderate rate of acceptance of intervention among high-scoring women in the intervention arm. The exploratory analyses include options for addressing the non-accepting completers in the prospective arm, and comparing them to those in mITT and the compliant completers.

The exploratory outcomes will be summarized within the prospective arm and within historical controls using descriptive statistics and graphical displays where appropriate. Continuous outcomes will be summarized using sample size (n), means, medians, standard deviations, and ranges. Categorical outcomes will be summarized using frequency and percentages. Estimates will be presented with 95% confidence intervals. Exploratory summaries will be performed for the mITT population.

The following exploratory endpoints will be evaluated by a test of proportions in the prospective arm versus historical controls. The null hypothesis is no difference between historical controls and the prospective arm. The alternative hypothesis is relative reduction in proportion of occurrence of one or more conditions in the prospective arm as compared to historical controls. Statistical testing for these endpoints will be performed using a logistic regression model with covariates as specified above for the primary analysis, and with propensity scoring adjustment as specified for the alternative analysis.

- Reduction in occurrence of one or more major neonatal morbidities with high likelihood of major chronic illness (MNM): cystic periventricular leukomalacia,

- grade 3 and 4 intraventricular hemorrhage, grade 3 or higher retinopathy of prematurity, bronchopulmonary dysplasia.
- Reduction in the rate of PTB <35 weeks, <32 weeks and <37 weeks of gestation. This analysis will be repeated for premature neonates delivered after spontaneous rupture of membranes or spontaneous onset of labor with gestational age at birth <32, <35 and <37 weeks vs. all other neonates.
- Reduction in NICU admission rates in the immediate neonatal period prior to initial discharge or neonatal death. This analysis will be repeated for all premature neonates, and for premature neonates delivered after spontaneous rupture of membranes or spontaneous onset of labor.

The following exploratory endpoints will be evaluated using a time-to-event analysis. The null hypothesis is no difference between historical controls and the prospective arm. The alternative hypothesis is shorter length of stay in the prospective arm as compared to historical controls. Statistical testing for this endpoint will be performed using a Cox proportional hazards regression model with covariates and stratification as specified above for the primary analysis, and with propensity scoring adjustment as specified for the alternative analysis. Length of hospital stay is adjusted to the maximum observed length of stay plus one for all instances of perinatal mortality. Length of NICU stay is adjusted to the maximum observed length of stay plus one for all instances of NICU mortality.

- Reduction in length of NICU hospital stay of all NICU admissions for premature neonates. For clarity, this analysis includes only PTBs with NICU admission. This analysis will be repeated for all premature neonates delivered after spontaneous rupture of membranes or spontaneous onset of labor.
- Reduction in length of NICU hospital stay (including zero-length stays for those not admitted) for all premature neonates from time of birth up to neonatal discharge. For clarity, this analysis includes PTBs independent of NICU admission, with stays for the non-admitted set to zero days. This analysis will be repeated for all premature neonates delivered after spontaneous rupture of membranes or spontaneous onset of labor.

- Reduction in length of neonatal hospital stay for all premature neonates from time of birth up to neonatal discharge. This analysis will be repeated for all premature neonates delivered after spontaneous rupture of membranes or spontaneous onset of labor.

As exploratory analyses, the primary and alternative analyses will be replicated, with the modification that the exploratory analyses will use multiple imputation and will include the candidate variables for which more than 5% of subjects have a missing value.

As exploratory analyses, the primary analysis will be replicated as a “raw” unadjusted analysis, with the modification that no covariates will be included in regressions.

As an exploratory analysis, a test of the proportional odds assumption for NMI data will be conducted. If the proportional odds assumption does not hold, we will examine the data using a set of separate logistic regressions or partial proportional odds models, to explicitly see how the odds ratios for the explanatory variables vary at the different thresholds. Alternatively, we will also apply the generalized logit model, which treats the response as nominal (unordered) rather than ordinal and has a full set of parameters for each generalized logit. We will then compare the results from proportional, fully nonproportional, and partial proportional odds models fitted to data.

As exploratory analyses, the primary analysis will be replicated, with the modification that the analysis will be restricted to prospective subjects with at least one propensity-matched control, and historical controls will be restricted to those propensity-matched to prospective subjects. At most 4 historical controls will be matched to each prospective subject. Matching algorithms will be chosen from among nearest neighbor matching, caliper matching with comparison units within a certain width of the propensity score of the treated units get matched, where the width is generally a fraction of the standard deviation of the propensity score; Mahalanobis metric matching in conjunction with propensity score matching (PSM), stratification matching, difference-in-differences matching (kernel and local linear weights), or exact matching. The matching method will

be chosen by the distribution of the propensity scores and the balance status of baseline characteristics.

As exploratory analyses, the primary and alternative analyses will be replicated using the ITT population. Subjects with missing data for required variables will be excluded from the analyses. To test if covariates are known to be misclassified under some approaches, an “intention to treat” analysis will be conducted that assumes that each participant continues to be exposed once they have received an initial treatment. Originally used in the analysis of randomized trials, this approach has been used in this hybrid study. It can be worthwhile to do a sensitivity analysis on studies that use an “intention to treat” approach to see how different an “as treated” analysis would be even if intention to treat is the main estimate of interest.

As exploratory analyses, the primary and alternative analyses will be replicated using the completers population with treatment covariates. Covariates for treatment modalities inclusive of use of aspirin or progesterone, will be included in the analyses if showing record of use between LMP and delivery in both the prospective arm and historical controls. Subjects with missing data for required variables will be excluded from the analyses. Subjects in the higher-risk group accepting interventions will be compared to non-intervention completers and to historical controls using descriptive statistics as described above. If use of any treatment is significantly associated with variables specified for the alternative analysis, this analysis will be repeated with inclusion of such variables as covariates in the analysis. Subjects with missing data for required variables will be excluded from this analysis.

As an exploratory analysis, the primary and alternative analyses will be replicated using the compliant completers population plus the not-higher-risk group as the preterm prevention arm for comparison to historical controls. Additional subgroup analysis of the compliant completers population will apply the primary, secondary and exploratory endpoints to subjects compliant with each component of the intervention versus all other compliant completers, and versus non-intervention completers. If compliance with any

treatment is significantly associated with variables specified for the alternative analysis, this analysis will be repeated with inclusion of such variables as covariates in the analysis. Subjects with missing data for required variables will be excluded from this analysis.

The use of antenatal corticosteroids will be assessed in relation to primary, secondary and exploratory endpoints, and will be compared between the preterm prevention arm and historical controls, and between higher risk and not higher risk subjects in the preterm prevention arm. Optimal timing of dosing of antenatal corticosteroids is herein defined as 2 to 7 days (inclusive) prior to delivery at less than 37 weeks of gestation. Use of antenatal corticosteroids will be expressed as a binary variable: were steroids given in the optimal interval between dose and delivery? Significance of interaction between optimally timed use of antenatal corticosteroids and the specified treatment groups will be assessed in regression as an interaction term: (binary variable) * group. This analysis will be performed without adjustment, adjusted for covariates as specified for the primary analysis, and adjusted via propensity scoring as specified for the alternative analysis. Missing values will be addressed as previously specified for exploratory analyses: by omission of subjects with missing values and by replicating the analysis with multiple imputation of missing values.

Primary, secondary and exploratory endpoints will be assessed in the prospective portion of the mITT population as dependent responses to nonrandom quantitative assignment of treatment⁴². The independent quantitative assignment variable will be the PreTRM® risk score. The functional relationship between endpoints and the risk score will be estimated for the prospective arm. A discontinuity at the intervention threshold in the relationship between outcome and risk score observed in the prospective arm will demonstrate intervention effect, measured as the estimated magnitude of the discontinuity and re-assessed as the estimated risk-score dependent difference between compliant completers and non-intervention completers. As this analysis involves only prospective subjects, it is independent of any selection biases or epoch effects present in comparisons of the prospective arm relative to historical controls. To adjust for any biases present within the

prospective arm, the analysis will be performed without adjustment, adjusted for covariates as specified for the primary analysis, and adjusted via propensity scoring as specified for the alternative analysis.

The primary, secondary and exploratory endpoints will be applied to comparisons within the mITT population.

- a) The higher-risk group will be compared to the not-higher-risk group within the prospective arm, for tests of equivalence. This comparison is independent of any selection biases or epoch effects present in comparisons of the prospective arm relative to historical controls.
- b) The not-higher-risk group of the prospective arm will be compared to historical controls to assess test sensitivity. It is expected that there will be significant differences in baseline characteristics between the two groups. The analysis will be performed without adjustment, adjusted for covariates specified for the primary analysis, and adjusted via propensity scoring as specified for the alternative analysis.
- c) The higher-risk group in the prospective arm will be compared to a control comparator group estimated as the difference between the control group and the not-higher-risk group, to assess efficacy of the intervention strategy. For count endpoints, direct subtraction of counts (adjusted for arm size) will be used to estimate the comparator group. For non-count endpoints, a number of most similar outcomes proportional to arm size will be removed from the control comparator group for each subject in the not-higher-risk group. It is expected that there will be significant differences in baseline characteristics between the two groups. The analysis will be performed without adjustment, adjusted for covariates specified for the primary analysis, and adjusted via propensity scoring as specified for the alternative analysis.

The following exploratory outcomes will be examined using only the descriptive statistics described above.

- Birthweight
- Number of days of mechanical ventilation

- Amount of surfactant administered
- Occurrence of birthweight <1500g and <2500g
- Individual components of composite morbidity/mortality index
- Whether or not a neonate received surfactant
- Occurrence of pneumonia
- Occurrence of 5-minute Apgar<7
- Occurrence of asphyxia
- Occurrence of preeclampsia
- Occurrence of gestational diabetes mellitus
- Rate of PPROM
- Rate of preterm delivery not associated with PPROM
- Baseline and on-treatment progesterone levels determined by LC-MS

Sensitivity analyses will be performed to check uncertainties in our analysis, as well as address basic assumption validation and the effect of unmeasured/unbalanced confounding factors on primary outcomes. The analyses will compare inclusion and omission of covariates in the analyses of primary, secondary and exploratory endpoints in the mITT population. As PTB is an outcome whose consequences are dominated by the lower tail of the gestational age distribution, sensitivity analyses will also examine the effect on effect size estimates of omitting outliers from the analyses.

A sensitivity analysis to control for reduction in subject number in the prospective arm of the mITT population will be performed. The primary and alternative analyses will be replicated as sensitivity analysis with bootstrap sampling of historical controls to the same number of subjects as the prospective arm. If exclusion of any completers from the mITT population is significantly associated with variables specified for the alternative analysis, this analysis will be repeated with such variables included as covariates. Subjects with missing data for required variables will be excluded from the covariate analysis.

A Bayesian Meta-Analysis will be performed on the data from this study and relevant previous studies. This will be described in a separate document.

Health Economic Outcomes:

Total cost of hospital care for each of the mother and neonate beginning at initiation of care through primary delivery and a gestational age of 40^{0/7} weeks in prospective vs. historical subjects. Analysis of these outcomes is covered in a separate SAP entitled SEAR.

